Official Title: Efficacy and Safety of Different Ticagrelor Regimens Versus Clopidogrel in Patients With Coronary Artery Disease: a Retrospective Multicenter Study (SUPERIOR)

NCT number: 03381742

Document date: August 16, 2019

Objective

Current guidelines favor dual anti-platelet therapy with ticagrelor 90 mg BID (T90BID) over clopidogrel 75 mg QD (C75QD) in addition to aspirin for coronary artery disease (CAD). However, an increased risk of ticagrelor-related adverse events prompted evaluation of low-dose regimens. This study aimed to examine the efficacy and safety outcomes of two low-dose regimens of ticagrelor in a large-scale cohort of patients with CAD.

Design

This is a retrospective, multicenter, observational study of 3,043 consecutive inpatients and outpatients with CAD, who received either ticagrelor or clopidogrel therapy.

Methods

We retrospectively analyzed the data from 11 hospitals on 3,043 CAD patients, who received C75QD, T90BID, ticagrelor 45 mg BID (T45BID), or ticagrelor 90 mg QD (T90QD) for at least 5 consecutive days before thromboelastography test. The main efficacy outcome was the ADP-induced inhibition of platelet aggregation (IPA), and other efficacy outcomes included ADP-induced platelet-fibrin clot strength (MA), rate of high on-treatment platelet reactivity (HTPR), and cardiovascular event (cardiovascular death, new-onset myocardial infarction, or stroke) rates. The primary safety outcome was bleeding rate (major or minor bleeding), and rate of new-onset dyspnea was also studied. All the patients had a 5-day follow-up period after the first dosing of study drugs to assess the efficacy and safety outcomes. The outcomes were compared between patients with clopidogrel treatment and patients who received different ticagrelor regimens (T90BID, T45BID and T90QD) using logistic regression model for total population and propensity score–matching analysis.

Primary data analysis was performed by investigators with cooperation from the First Affiliated Hospital of Harbin Medical University and the other participating hospitals. The study was approved by the Ethics Committees of the First Affiliated

Hospital of Harbin Medical University.

Data are summarized as frequencies and percentages for categorical variables. Continuous variables are expressed as median and interquartile range. To compare differences in continuous variables among groups, Mann–Whitney U test or Kruskal–Wallis rank sum test was performed, followed by Dunn’s multiple comparison test. The Fisher’s exact test or χ^2 test was used to compare categorical variables, followed by Bonferroni adjustments for multiple comparisons test. Univariate and multivariate logistic regression analyses were conducted to evaluate the association between platelet inhibition (HTPR/non-HTPR) and treatment group or other clinical characteristics. Odds ratios (OR) and their 95% confidence intervals (CIs) are presented as a measure of association.

Propensity score matching was performed to reduce selection bias and confounders between two groups at baseline. The propensity scores were estimated using a multivariate logistic regression model that included the following variables: age; gender; weight; cigarette smoking; hypertension; diabetes mellitus; chronic kidney disease; previous PCI; previous coronary artery bypass grafting; serum levels of total cholesterol, triglycerides, high-density lipoprotein, low-density lipoprotein, creatinine and uric acid; aspirin use; and acute myocardial infarction. The propensity scores were used to match the clopidogrel and ticagrelor groups in a 1:1 ratio, with a caliper value of 0.05.

All statistical analyses were 2-tailed, and a *P* value < 0.05 was considered statistically significant. Statistical analyses were performed using SAS software version 9.4 (SAS Institute, Cary, NC, USA) and R version 3.2.1 (<http://www.r-project.org>).

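### Inpatients and outpatients are pooled but care setting is not in the propensity model, so regimen differences may be confounded by setting

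*Combined protocol and SAP*

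**What the plan says.** The Design section defines the cohort: "This is a retrospective, multicenter, observational study of 3,043 consecutive inpatients and outpatients with CAD". The Methods section adds the source, "We retrospectively analyzed the data from 11 hospitals on 3,043 CAD patients", and the exposure rule, which requires a study regimen "for at least 5 consecutive days before thromboelastography test". IPA is the main efficacy outcome. On safety it says: "The primary safety outcome was bleeding rate (major or minor bleeding), and rate of new-onset dyspnea was also studied". On follow-up: "All the patients had a 5-day follow-up period after the first dosing of study drugs to assess the efficacy and safety outcomes". How doses were verified and how events were found is not described for either setting.

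The propensity paragraph of the (unheaded) statistical text introduces its covariates with "The propensity scores were estimated using a multivariate logistic regression model that included the following variables". The list begins "age; gender; weight; cigarette smoking; hypertension; diabetes mellitus; chronic kidney disease; previous PCI; previous coronary artery bypass grafting". It continues with six laboratory measurements and ends with aspirin use and acute myocardial infarction. Matching is 1:1 on that score with a caliper of 0.05.

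Continuous outcomes are compared with rank tests. The one regression described in detail has HTPR status as its outcome, with treatment group and unlisted clinical characteristics as predictors. The Methods section also mentions logistic regression in the total population, without covariates.

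**The concern.** Matching on a score balances a variable outside the score only as far as that variable is correlated with those inside it. Care setting is a distinction the design itself draws, and it could plausibly influence both sides of the comparison. It reflects how acutely ill a patient is, which can steer the choice of regimen. It could also affect whether the five days of treatment were fully taken, and whether minor bleeding or breathlessness reached a record that was later read retrospectively.

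Acute myocardial infarction carries part of this information, but an inpatient without infarction and a stable outpatient share the same value. If setting differs between regimens after matching, part of an apparent difference in IPA, HTPR, bleeding or dyspnea could belong to setting and not to the drug. The primary safety outcome includes minor bleeding, the component most open to unequal recording. A common five-day window equalises the length of follow-up but not the completeness of recording.

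**Working it through.** The plan has no figure of its own to reproduce: 3,043 is the observed cohort size, and no power or event calculation is given.

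**Step 1: is setting handled anywhere?**
- Propensity list: 9 demographic and history items + 6 laboratory values + aspirin + acute myocardial infarction = 17. Items that record inpatient/outpatient status: 0.
- IPA: the named tests (Mann–Whitney, Kruskal–Wallis, Dunn) carry no covariates, so matching is the only adjustment described for the main efficacy outcome.
- HTPR: the regression covariates are not fully listed. Setting could be among them, but it is not named.
- Bleeding and dyspnea: no covariate list is given.

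**Step 2: how large could the bias be?** Every input here is an assumption, since the documents give no split by regimen, no adherence data and no rates of event recording.

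*IPA.* Bias in the mean = (inpatient minus outpatient IPA) × (difference between arms in inpatient share).
- No imbalance: any setting effect × 0 = 0 points.
- Small case: 2 points × 0.10 = 0.2 points.
- Middle case: 5 points × 0.30 = 1.5 points.
- Large case: 10 points × 0.50 = 5.0 points.

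*Recorded events, true rates equal.* Apparent ratio = [a + (1 − a)c] / [b + (1 − b)c], where a and b are the inpatient shares in the two arms and c is outpatient recording relative to inpatient recording.

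| a | b | c | Apparent ratio |
|---|---|---|---|
| 0.7 | 0.7 | any | 1.00 |
| 0.8 | 0.6 | 0.9 | 0.98/0.96 = 1.02 |
| 0.8 | 0.6 | 0.7 | 0.94/0.88 = 1.07 |
| 0.8 | 0.6 | 0.5 | 0.90/0.80 = 1.13 |
| 0.9 | 0.5 | 0.5 | 0.95/0.75 = 1.27 |

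A harsher set (80% v 40% inpatients, with 90% of inpatient and 40% of outpatient events recorded) gives (0.8 × 0.9 + 0.2 × 0.4) / (0.4 × 0.9 + 0.6 × 0.4) = 0.80/0.60 = 1.33.

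**Step 3: would that matter to a test?** Assume 500 patients per matched arm, a normal approximation and no true effect.
- IPA, assumed SD 25, bias 2 points: standardised shift 2 / (25 × √(2/500)) = 1.26. A two-sided 5% test then rejects about 24% of the time.
- Events, true rate 5%, a = 0.9, b = 0.5, c = 0.5: recorded rates are 4.75% v 3.75%, with rejection about 12%.
- Events, true rate 5%, a = 0.8, b = 0.6, c = 0.7: recorded rates are 4.7% v 4.4%, with rejection about 6%.

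The consequence therefore runs from none to material, depending on a split that the documents do not show.

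**The case against.** The strongest reply is that an omission is not a bias. Confounding needs the inpatient share to differ between regimens after matching, and nothing in the documents shows that it does. A pair made of one inpatient and one outpatient is harmless in itself, because such pairs can run in both directions; only the net imbalance counts. Acute myocardial infarction, previous PCI and fifteen other variables may already remove much of any imbalance. The entry rule requires five consecutive days of treatment, so a patient known to have missed doses would not qualify as written. All patients are said to have had the same follow-up. The HTPR model may include setting.

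Most of this stands, and it limits the claim. A reader might infer that the regimen comparisons are in fact mixed with setting, or that ticagrelor looks both more potent and less safe than it is. The documents support neither, because they give no split and hence no direction. A reader might also infer that inpatient doses were supervised, that outpatient dosing was self-reported, or that outpatient bleeding went unrecorded. These are reasonable possibilities, but none is stated.

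The IPA figures are shifts in the mean, whereas the plan reports medians and rank tests, and no effect size is given to set them against. The event illustration concerns outcomes whose recording could vary; it should not be carried over to cardiovascular events.

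The reply does not supply any stated handling of setting. Even if the HTPR model includes it, that would not adjust IPA, bleeding or dyspnea.

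**Conclusion.** The gap is real and worth correcting. The plan pools two care settings and states no step that deals with them, so comparisons of IPA, HTPR, bleeding and dyspnea may be confounded by setting. Whether they are, in which direction and by how much cannot be determined from the documents. Bias is zero if setting is balanced after matching. Under the assumed inputs above, it reaches an apparent event ratio of about 1.3 and about 5 IPA points, and those upper ends need imbalances of 40 to 50 percentage points to persist after matching. That setting is available for each patient is itself inferred from the design sentence.

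**What to change.** - Add inpatient/outpatient status to the propensity model, or match exactly on it and apply the 0.05 caliper within setting. Define it at first dose so that it is a baseline variable, bearing in mind that it does not measure supervision over the following days.
- Include it in the adjusted logistic models, and list those models' covariates.
- Tabulate setting for each regimen before and after matching, with standardised differences. This table alone would show whether the concern has any force.
- State how adherence and events were ascertained in each setting.
- Report bleeding and dyspnea by setting as a sensitivity analysis. Making inpatients the primary safety population is not recommended, since it changes the target population before any imbalance has been shown.

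Cost: no new data collection if setting is recorded for each patient. The statistical text describes the matching as already done, so the change means rerunning the matching and the analyses that depend on it, with some loss of matched pairs.

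### Clinical events are counted over the same 5 days a patient must complete to enter the cohort, so cardiovascular death is essentially unobservable and the other event rates describe only patients who completed the regimen and were tested

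*Combined protocol and SAP*

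**What the plan says.** All references are to the combined protocol and SAP.

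- **Entry (Methods).** Patients received one of four regimens "for at least 5 consecutive days before thromboelastography test".
- **Outcome window (Methods).** "All the patients had a 5-day follow-up period after the first dosing of study drugs to assess the efficacy and safety outcomes".
- **Clinical outcomes (Methods).** Efficacy includes "cardiovascular event (cardiovascular death, new-onset myocardial infarction, or stroke) rates". For safety: "The primary safety outcome was bleeding rate (major or minor bleeding), and rate of new-onset dyspnea was also studied".
- **Comparison (Methods).** "The outcomes were compared between patients with clopidogrel treatment and patients who received different ticagrelor regimens", by logistic regression in the total population and by propensity score matching.
- **Population (Design).** The cohort is "3,043 consecutive inpatients and outpatients with CAD, who received either ticagrelor or clopidogrel therapy".
- **Purpose (Objective).** The reason given for the study is that "an increased risk of ticagrelor-related adverse events prompted evaluation of low-dose regimens".

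The propensity-score paragraph of the statistical text lists patient characteristics, history, laboratory values, aspirin use and acute myocardial infarction as matching variables. None of them records whether a patient stayed on the regimen or reached TEG. Nothing in the documents mentions patients who died, stopped or switched before TEG, or says what the entry rule implies for the clinical event rates.

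**The concern.** The entry rule suits a platelet-function outcome, which needs a period on treatment and a test result. The clinical outcomes are different. They are counted from the first dose, over a period the patient must already have completed on treatment to be included. An event that kills the patient, ends treatment early or prevents the test removes both the event and the patient from the analysis.

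Two things are at stake. A reader who sees no cardiovascular deaths under any regimen could take that as reassurance, although the entry rule produces it. And bleeding and dyspnea, which bear directly on the stated reason for studying low doses, are seen only in patients who stayed on the regimen long enough to be tested. Adverse events that stop treatment early are the ones this cohort can miss.

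**Working it through.** The plan gives no event rate, loss count or power figure on this point, so there is no figure to reproduce. The number 3,043 is a count of included patients.

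**Step 1: the windows.** Take time 0 as the first dose of the qualifying regimen, which is the natural reading of the Methods.

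- Event window: day 0 to day 5.
- Entry condition: alive, on the regimen, and tested at some day t of 5 or later.
- Follow-up left in the window after the earliest qualifying TEG: 5 − 5 = 0 days.

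A death can be counted only if it falls after TEG and by day 5. That requires TEG at t = 5 and death later that same day.

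**Step 2: the observed rate.** Let p be the true 5-day risk, s the share of patients with an event who are lost before inclusion, and u the share of event-free patients lost before inclusion. Then

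observed rate = p(1−s) / [p(1−s) + (1−p)(1−u)].

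For a death before TEG, s = 1 and the observed rate is 0 whatever p is. This needs no assumed value. For other events s can be below 1, because an event that neither ended treatment nor prevented the test is still counted.

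**Step 3: the comparison between regimens.** With C for clopidogrel and T for a ticagrelor regimen,

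observed OR = true OR × [(1−sT)/(1−sC)] × [(1−uC)/(1−uT)].

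The multiplier is 1 exactly when the retention ratio (1−s)/(1−u) is the same in both groups. Unequal loss of patients with events is therefore neither necessary nor sufficient for bias.

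**Step 4: illustration.** Every value of p, s and u here is an assumption; none is in the documents. Take 5-day bleeding risks of 2% (C) and 4% (T). The true OR is (0.04/0.96)/(0.02/0.98) = 2.04.

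| s, C/T | u, C/T | Multiplier | Observed OR |
|---|---|---|---|
| 5%/10% | 0%/0% | 0.90/0.95 = 0.947 | 1.93 |
| 5%/10% | 5%/10% | 0.947 × 0.95/0.90 = 1 | 2.04 |
| 10%/28% | 0%/20% | (0.72/0.90) × (1/0.80) = 1 | 2.04 |
| 10%/10% | 10%/20% | 0.90/0.80 = 1.125 | 2.30 |
| 10%/10% | 20%/10% | 0.80/0.90 = 0.889 | 1.81 |

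Rows two and three have unequal event loss and no distortion. Rows four and five have equal event loss and distortion in opposite directions.

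The absolute rate can also move either way. At a true 4% with s = 10%, the observed rate is 0.036/(0.036 + 0.96) = 3.61% if u = 0%, 4.00% if u = 10%, and 0.036/(0.036 + 0.768) = 4.48% if u = 20%.

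**The case against.** The strongest reply is that the restriction is disclosed. The Methods state the 5-day and TEG requirement openly, and a careful reader can see that every outcome is conditional on it. The document is a short methods summary with no results or limitations section, so nothing shows that a later report would omit the caveat. This stands as far as the rule itself goes. But disclosing an entry rule for a platelet test does not tell readers that it fixes deaths near zero and conditions the safety rates.

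Four further replies are correct and limit the point.

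- The word consecutive in the Design section can fairly mean consecutive eligible patients. A reader might infer that it contradicts the entry rule; it need not.
- Bias between regimens is not shown. The scenarios above show only that it is possible, and the documents favor none of them.
- Matching is not irrelevant. Loss explained by matched covariates such as age, kidney disease or acute infarction can be handled by it. Loss driven by the event itself or by unmeasured factors cannot.
- The platelet outcomes are not cleared. The overlap of windows does not touch IPA, MA or HTPR, but those are also measured only in patients who completed 5 days and had TEG.

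**Conclusion.** The point holds, and it should be fixed. On the natural reading of the two Methods sentences, the event window closes at or before the earliest qualifying TEG. Cardiovascular death is essentially zero by design in every group, and the rates of bleeding, dyspnea, infarction and stroke apply only to patients who stayed on the regimen and reached TEG. A safety conclusion about the regimens in everyone who started them would not be supported.

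Confidence is high for these two statements. They assume only that the first dose is the start of the qualifying regimen.

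The size and direction of any bias in the odds ratios, or in the absolute non-fatal rates, are undetermined and may be nil. A reader might infer that the ticagrelor regimens are made to look safer than they are. The documents do not support that: they give no loss figures and do not say how patients came to have TEG. A reader might equally infer that the main efficacy outcome is sound because the overlap leaves it untouched. That is not established either, since IPA carries the same selection.

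**What to change.** Keep the cohort and all outcome definitions, and make three changes of wording and reporting.

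1. Report bleeding, dyspnea, myocardial infarction and stroke as conditional on completing at least 5 days of the regimen and having TEG, and limit the safety conclusion to those patients.
2. State that cardiovascular death is essentially unobservable under the entry rule. Interpret the composite as mainly non-fatal infarction or stroke, and draw no inference about mortality.
3. Note that IPA, MA and HTPR are conditional on the same requirement.

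This needs no new patients or data. Its price is a more modest safety claim, and it discloses the selection without removing it.

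Optional, and not part of this low-cost change: where hospital records allow, a sensitivity analysis of all patients who started each regimen, classified by the regimen at first dose, with the numbers lost before day 5 or without TEG by regimen and reason. That is a different cohort and needs new extraction of records.

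### Bonferroni on the categorical comparisons is valid, but Holm's step-down procedure on the same comparisons keeps the 0.05 familywise bound and never rejects less

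*Combined protocol and SAP*

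**What the plan says.** The first paragraph of the statistical analysis text (unheaded, after Methods) compares categorical variables by Fisher's exact or chi-square test, "followed by Bonferroni adjustments for multiple comparisons test". It does not say how many comparisons the adjustment covers and names no outcome. The general rule is that "All statistical analyses were 2-tailed" and that a P "value < 0.05 was considered statistically significant".

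Methods supplies the outcomes. On safety: "The primary safety outcome was bleeding rate (major or minor bleeding), and rate of new-onset dyspnea was also studied". HTPR and cardiovascular events are also reported as rates. All four are categorical, so the Bonferroni sentence reaches them by inference.

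Methods also gives the comparison: "The outcomes were compared between patients with clopidogrel treatment and patients who received different ticagrelor regimens (T90BID, T45BID and T90QD"). That makes three contrasts with clopidogrel; four groups make six possible pairs. The same sentence assigns the comparison to logistic regression and propensity score matching. No multiplicity correction is stated for either.

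**The concern.** Bonferroni holds every comparison to the strictest threshold, including those examined after others in the family have already been rejected. Holm relaxes the threshold step by step as rejections accumulate, without raising the familywise bound. On any fixed family of tests Bonferroni can therefore miss a difference that Holm would report, and it never finds one that Holm would miss.

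This matters most for bleeding and dyspnea. The Objective says that concern over adverse events on ticagrelor led to the study of the low-dose regimens. If the full-dose regimen shows an excess first, the contrasts that gain from Holm are likely to be the low-dose ones. Follow-up is short ("All the patients had a 5-day follow-up period after the first dosing of study drugs"), so events may be few and power is worth keeping.

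**Working it through.** **Inputs from the documents.** Four groups; two-sided alpha 0.05; Bonferroni with an undefined family; total sample from "observational study of 3,043 consecutive inpatients and outpatients with CAD". No power calculation, arm sizes or expected rates are given, so there is no figure of the plan's to reproduce.

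**Inputs assumed.** Arms of 1543/500/500/500 (clopidogrel, T90BID, T45BID, T90QD; sum 3,043) and bleeding of 2% versus 4.5/4/4%. Other assumptions are tried below.

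**Thresholds.** Bonferroni uses 0.05/m throughout. Holm orders the m p-values, compares the k-th smallest with 0.05/(m − k + 1), and stops at the first failure.

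| Family | Bonferroni | Holm, in order |
|---|---|---|
| m = 3 | 0.0167 | 0.0167, 0.025, 0.05 |
| m = 6 | 0.0083 | 0.0083, 0.0100, 0.0125, 0.0167, 0.025, 0.05 |

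**Why no rejection is lost.** If a p-value is at most 0.05/m, so is every smaller one, and each Holm threshold is at least 0.05/m. Holm therefore reaches that p-value and rejects it.

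**Why the bound is kept.** With m0 true nulls, at most m − m0 rejections can precede the first false one. The threshold there is at most 0.05/m0, and the chance that any of m0 null p-values falls below 0.05/m0 is at most 0.05. Independence is not needed.

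**Power.** 200,000 simulated data sets per scenario; pooled two-sided z test for two proportions (the uncorrected chi-square). Under the assumed arms and rates:

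| Rule | Power per contrast with clopidogrel | All three detected | At least one detected |
|---|---|---|---|
| Bonferroni, 3 contrasts | 71/53/53% | 26.4% | 89.1% |
| Holm, 3 contrasts | 76/61/61% | 41.5% | 89.1% |
| Bonferroni, 6 pairs | 63/44/44% | 18.7% | 82.8% |
| Holm, 6 pairs | 65/47/47% | 22.1% | 82.8% |

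With the family held fixed, the gain per contrast is about 5 to 8 points for three contrasts and about 1.5 to 2.5 points for six pairs. No Bonferroni rejection was lost in any replicate.

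**Other assumptions, three contrasts, Bonferroni to Holm.**
- Equal arms (about 761 each), 3% versus 6/6/6%: 67% to 75% per contrast; all three 43% to 61%; at least one 88.5% under both.
- Arms 1800/843/200/200, 3% versus 6/5/5%: low-dose contrasts 23% to 29%.
- Arms 1543/500/500/500, one regimen harmful (2% versus 4.5/2/2%): 71.2% to 71.3%.
- Same arms, small low-dose excess (2% versus 4.5/2.5/2.5%): low-dose contrasts about 6% to 7.5%.

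**Realised error on true nulls, three contrasts, one regimen harmful (3% versus 6/3/3%).** 3.0% to 3.9% with equal arms; 3.1% to 4.6% with 1800/843/200/200. Both stay under 5%.

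**The case against.** The strongest reply is that nothing here is wrong: Bonferroni controls the familywise error, and preferring Holm is a matter of efficiency. That stands, and it limits the weight of the point.

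A reader might infer that each comparison is judged at 0.0083 because all six pairs are tested, and that cutting the family to three would lift the chance of detecting all three excesses from 19% to 42%. The documents do not support this. The family is not stated, and Methods fits three contrasts at least as well. The rise also mixes two changes: 18.7% to 26.4% (7.7 points) comes from the smaller family, and 26.4% to 41.5% (15.1 points) from Holm. Nor is cutting the family free. The Objective makes low-dose versus full-dose ticagrelor a natural safety question, so those pairs are not idle. If those two pairs were added to the three contrasts, Holm over five would detect all three excesses in 25.9%, with 67/50/50% per contrast.

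A reader might also infer that Holm detects more harm at no cost. Within three contrasts it adds a finding only once another contrast has passed 0.0167. The costs are small but real. Bonferroni has simple matching simultaneous intervals and Holm does not, although the plan states only ordinary 95% intervals for its odds ratios. Realised error can rise within the bound. The study is retrospective and the document is written in the past tense, so a switch now may come after results are known.

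Finally, the regression analyses of the outcomes lie outside the Bonferroni sentence. This also stands: the change does not touch them.

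**Conclusion.** The point holds as a modest efficiency improvement and not as an error. For any fixed family, Holm keeps the 0.05 familywise bound and rejects everything that Bonferroni rejects, and sometimes more. That result needs no assumption about rates or arm sizes.

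The size of the gain does need them. It is about 5 to 8 points per contrast for three contrasts and 1.5 to 2.5 points for six pairs under the main assumed scenario. It is close to nothing for three contrasts when one regimen alone is harmful. Fisher's exact test with few events would give lower power under both rules.

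The documents do not support the inference that the planned correction makes a ticagrelor regimen look safer than it is. Bonferroni's application to bleeding and dyspnea is itself inferred, and the confounder-adjusted comparisons carry no stated correction.

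**What to change.** In the first paragraph of the statistical analysis text, replace the Bonferroni adjustment with a *Holm step-down adjustment over the same set of comparisons*. The family need not be cut, but the sentence should state which comparisons it contains, because the thresholds depend on that number.

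The cost is one sentence. The authors give up simple matching simultaneous intervals, which the plan does not state in any case. They also accept a slightly higher realised error on true nulls, within 5%. If results are already known, the change should be reported as made afterwards, with the Bonferroni results shown alongside.

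The change applies to the Fisher and chi-square comparisons only. The plan should say separately whether the logistic regression and matched analyses are adjusted for multiplicity.

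### Hospital is absent from the propensity model, the matching rule and every named group test in this 11-hospital non-randomised study

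*Combined protocol and SAP*

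**What the plan says.** All references are to the combined protocol and SAP.

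- **Methods, data source:** "We retrospectively analyzed the data from 11 hospitals on 3,043 CAD patients". The Design section describes the study as retrospective and observational, so regimen was chosen in practice and not allocated.
- **Methods, comparison:** clopidogrel is compared with each ticagrelor regimen "using logistic regression model for total population and propensity score–matching analysis".
- **Statistical text (unheaded), purpose of matching:** "Propensity score matching was performed to reduce selection bias and confounders between two groups at baseline".
- **Statistical text, propensity model:** "The propensity scores were estimated using a multivariate logistic regression model that included the following variables: age; gender; weight". The list runs on to acute myocardial infarction and has 17 items, all at patient level. Its wording is closed, with nothing to suggest that these are only examples.
- **Statistical text, matching rule:** "The propensity scores were used to match the clopidogrel and ticagrelor groups in a 1:1 ratio, with a caliper value of 0.05". There is no within-hospital condition.
- **Statistical text, group tests:** for continuous variables "Mann–Whitney U test or Kruskal–Wallis rank sum test was performed", with Dunn's test afterwards; for categorical variables Fisher's exact or chi-square with Bonferroni. None is stratified.
- **Statistical text, regression:** univariate and multivariate logistic regression is described for HTPR only, with clinical covariates that are not listed.

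Hospitals are otherwise mentioned only in connection with who ran the analysis and ethics approval. No site effect, clustered standard error or sensitivity analysis by site is described.

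**The concern.** In a non-randomised multicentre study, hospital can be a confounder in its own right. Hospitals may differ in how often they used each of the four regimens. They may also differ in outcome, in how thromboelastography was run and read, or in how completely bleeding, dyspnoea and cardiovascular events were recorded. If both kinds of difference exist and the 17 patient characteristics do not account for them, a hospital difference can pass for a regimen effect or hide a real one.

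This reaches the main efficacy outcome. IPA is a thromboelastography measure, and the only tests named for continuous variables are unstratified rank tests. With 11 hospitals, chance associations between regimen mix and hospital outcome level need not average out.

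**Working it through.** **What the documents control.**

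| Analysis | Hospital included? |
|---|---|
| Propensity model | No: closed list of 17 patient-level items |
| 1:1 matching, caliper 0.05 | No: score only |
| Mann–Whitney, Kruskal–Wallis with Dunn (IPA, MA) | No |
| Fisher's exact, chi-square (categorical) | No |
| Logistic regression for HTPR | Not stated: covariates not listed |

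The plan gives no arm sizes, outcome SD, regimen mix by hospital or between-hospital correlation. There is no figure of its own to reproduce.

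**Illustration: crude unmatched test.** From the documents: 11 hospitals and two-sided 0.05. Assumed: N = 1,900 in one contrast, share on one regimen p = 0.21, equal hospital sizes, hospital share distributed Beta(0.21k, 0.79k), normal hospital effect with intra-hospital correlation (ICC) 0.01 to 0.05, outcome SD 1, no regimen effect. *Mild* is k = 20 (10th to 90th percentile of hospital share 10% to 33%); *moderate* is k = 4 (2% to 48%).

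1. Variance of the crude difference: s² = 1/(1,900 × 0.21) + 1/(1,900 × 0.79) = 1/399 + 1/1,501 = 0.00317, so s = 0.056.
2. Variance of the hospital share: V = 0.21 × 0.79/(k + 1). Mild: 0.1659/21 = 0.0079. Moderate: 0.1659/5 = 0.0332.
3. Variance of the bias: b² = ICC × 10 × V/(11² × 0.1659²), with denominator 3.33. The bias can have either sign.
4. True variance relative to what the test assumes: R = 1 − ICC + b²/s².
5. False-positive rate: 2 × [1 − Φ(1.96/√R)].

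For moderate variation at ICC 0.05: b² = 0.05 × 10 × 0.0332/3.33 = 0.00498, b = 0.071; R = 0.95 + 0.00498/0.00317 = 2.52; 1.96/√2.52 = 1.235; rate 21.7%.

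| Variation in mix | ICC | b (outcome SDs) | R | Formula | Simulated, crude | Simulated, van Elteren |
|---|---|---|---|---|---|---|
| None | 0.01 | 0 | 0.99 | 4.9% | 4.9% | 4.9% |
| None | 0.05 | 0 | 0.95 | 4.4% | 5.4% | 5.3% |
| Mild | 0.01 | 0.015 | 1.07 | 5.8% | 5.7% | 4.8% |
| Mild | 0.05 | 0.034 | 1.32 | 8.9% | 9.2% | 4.7% |
| Moderate | 0.01 | 0.032 | 1.30 | 8.6% | 8.9% | 5.0% |
| Moderate | 0.05 | 0.071 | 2.52 | 21.7% | 21.5% | 5.0% |

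The simulation used 10,000 runs per cell (Monte Carlo standard error about 0.2 points at 5%). The formula ignores sampling variation in each hospital's realised mix, so small differences are expected.

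**After matching.** One case-mix score stands in for the 17 covariates, hospital is left out of the propensity model, and the caliper is taken on the probability scale, which the plan does not specify. About 22% are treated in these runs, not exactly 21%, because the case-mix score shifts the share. Mann–Whitney rates over ICC 0.01 to 0.05:

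| Hospital variation in mix explained by measured characteristics | Mild | Moderate |
|---|---|---|
| None | 5.3–7.3% | 6.6–15.3% |
| Half | 4.5–5.9% | 5.1–9.8% |
| All | about 4% | about 4% |

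With the same mix everywhere the matched rate is 4% to 5%.

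**Sparse events.** With 1,900/11 = 173 patients per hospital and an assumed 5-day risk r, the expected number of hospitals with no event is 11 × (1 − r)^173: 4.6 at 0.5%, 1.9 at 1%, 0.3 at 2%. This bears on the choice of method in the fix.

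**The case against.** **The harm is conditional.** Bias needs regimen mix and outcome (or its measurement) both to vary by hospital, beyond characteristics that already include acute myocardial infarction, previous PCI and creatinine. The documents show neither. This stands: the omission is certain, but its effect is not demonstrated.

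**The figures rest on assumptions.** This also stands. Under other assumptions (all 3,043 patients, equal arms, wider spreads, ICC up to 0.10) rates above 40% can be produced, which shows how little the number says about this particular trial. Only the mechanism carries over: no inflation with equal mix, inflation when both vary, and correction by stratification.

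**The effect may be small.** In the main scenarios the typical bias (one SD) is at most about 0.07 outcome SDs, and mild variation after matching gives 4.5% to 7.3%. No expected regimen effect is stated, so nobody can say that a conclusion would change. That limits the severity but does not close the gap.

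**The regression may already adjust.** A reader might infer that hospital is uncontrolled in every analysis. The documents do not support that for HTPR, because the covariates of that regression are not given. The Methods section mentions logistic regression for the outcomes generally, but the statistical text describes it only for HTPR. It therefore does not rescue IPA or MA, nor does it alter the matching.

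**Conclusion.** The point holds for the matched comparisons and for the unmatched tests of IPA, MA and categorical outcomes: as written, they do not control for hospital differences beyond the listed patient characteristics. For the HTPR regression, control is unreported.

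A reader might go further and infer that the reported regimen comparisons are biased. The documents do not support that. They give no data by hospital, and the bias is nil if the mix is the same everywhere or is fully explained by the 17 characteristics. Under the assumed inputs the crude false-positive rate is about 6% to 9% with mild and 9% to 21% with moderate variation, and it is smaller after matching when measured characteristics explain part of the variation. These figures illustrate the mechanism and do not estimate this trial's error rate. I would class the point as a cheap improvement.

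**What to change.** 1. Tabulate regimen by hospital, and report which hospitals, with how many patients, used a single regimen. This shows whether the first condition for bias is met.
2. Add hospital to the propensity model, or match within hospital. In the second case, exclude from each contrast the hospitals that used only one of its two regimens, and report them.
3. In the total population, stratify by hospital: van Elteren for IPA and MA, Cochran–Mantel–Haenszel for categorical outcomes.
4. List the covariates of the HTPR logistic model and include hospital.
5. For cardiovascular events and bleeding, where "All the patients had a 5-day follow-up period after the first dosing of study drugs" and several hospitals may have no event, use a stratified or conditional method in place of 11 fixed effects.
6. Label all of this post hoc, since the document already reports that "Primary data analysis was performed by investigators".

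Paired tests on hospital-blind pairs are no substitute: with moderate, unexplained variation the signed-rank test still rejected in 7.2% to 15.7% of runs.

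**Cost.** New SAP wording and a re-run, provided that the pooled file holds a hospital identifier, which the documents do not state. Some precision is lost. In the unmatched illustration the share of treatment variance left within hospitals is 1 − (10/11)/(k + 1), which is 0.957 (mild) or 0.818 (moderate), so the standard error rises by a factor of 1/√0.957 = 1.02 or 1/√0.818 = 1.11. The loss is larger if many hospitals used one regimen, and within-hospital matching then also narrows the population to which the result applies.
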